## **Patient-reported adherence**

### *Specific measure:*

Patients will fill out a study-specific PRO questionnaire, where they report their self-reported adherence (as measured by rate of days where a rash was apparent and the patient applied the prescribed topical preparation (from grade 1-4; 1: applied 0-25% of days, 2: applied 26-50% of days, 3: applied 51-75% of days, 4: applied 76-100% of days)). The study-specific adherence measure has previously been used by the research group (8).

### *Specific metric:*

Value at time-point at last patient visit.

### *Time point:*

At last study visit at week 48.

## **Disease severity measures**

### **Severity of psoriasis**

#### *Specific measure:*

Disease severity will be objectively measured by BSA (an interval scale from 0-100; 0, no involvement; 100, full body involvement) and LS-PGA (an ordinal scale from 1-8: 1, clear; 8, severely affected) (31).

Disease severity measures will be obtained by a blinded data assessor (a skilled nurse or a qualified trained research assistant). At the appointment the patient is put into a room; the blinded assessor sees the patient first and fills out the scoring (BSA and LS-PGA) – the patient is instructed not to talk except to exchange greetings. The person providing the rating inserts the scoring in the electronic research data capture system.

#### *Specific metric:*

Change from baseline.

*Method of aggregation:*

Mean.

*Time-point:*

Baseline and weeks 12, 24, 36 and 48.

### **Dermatology specific quality of life measure**

*Specific measure:*

The patient fills out a Danish translation of the PRO DLQI questionnaire (an ordinal scale from 0-30: 0, not affected by psoriasis; 30, severely affected by psoriasis) (32) questionnaire on a tablet, that synchronizes data into the data capturing tool.

*Specific metric:*

Change from baseline.

*Method of aggregation:*

Mean.

*Time-point:*

Baseline and weeks 12, 24, 36 and 48.

### **Generic health-related quality of life measure**

*Specific measure:*

The patient fills out a Danish translation of the PRO EQ-5D-3L questionnaire on a tablet, that synchronizes data into the data capture tool. EQ-5D-3L comprises five dimensions: mobility, self-care, usual activities, pain/discomfort and anxiety/depression. Each dimension has 3 levels: no problems, some problems, and extreme problems. The EQ-5D-3L health profiles are converted into a value based on the danish societal value sets (33). The EQ-5D value is on a scale where 1 represents full health and 0 represents being dead; the

higher the value, the better the health state. The scale allows negative values to be assigned to health states that are considered worse than dead.

*Specific metric:*

Change from baseline.

*Method of aggregation:*

Mean.

*Time point:*

Baseline and week 48.

## **Participant timeline**

The study will be concluded when the last included participant has completed the study.

Regarding PRO assessments, the initial PRO will be collected prior to randomization. PROs will be collected after the clinical assessments. At the visit at baseline and week 48, DLQI questionnaires will be obtained before the EQ-5D questionnaire. At visit week 48, patient-reported adherence will be reported after the EQ-5D questionnaire.

## **Study plan and design**

At an ordinary consultation with patients referred to the dermatology department, the investigator will screen for suitable participants according to the inclusion criteria. Before patients are included in the study, informed consent will be obtained at the baseline visit.

## **Information obtained and provided throughout the study**

At the baseline visit, the investigator will collect information from the patient on 1) current and previous use of medicine, 2) length of illness, 3) socio-economic status (marital status, educational level, days of sick leave and income), and 4) severity of disease and disease duration. The information will be used to check that the

non-intervention and intervention groups are comparable. In addition, after visit week 48, data from the Danish Health Registries will be obtained in order to have outcomes for primary adherence and costs of health service use.

## **Sample size**

The null hypothesis is that there is no difference in the primary outcome (LS-PGA) between the intervention and non-intervention groups. The sample size was calculated based on data from a previous project obtaining LS-PGA data from 134 patients randomized to intervention (an adherence-supporting app) or non-intervention (receiving standard-of-care support) (8), where an over 20% LS-PGA improvement in favour of the adherence-support intervention was observed between non-intervention and intervention group. A relative 20% difference in mean scale on the LS-PGA is expected, and a power of 80%, two-sided significance level of 95%, and 1:1 allocation is desirable, considering a maximum expected dropout rate of 80%. Based on mean and standard deviations of LS-PGA from the previous study this results in a maximum sample size for a two-sided t-test consisting of 115 participants before drop-out. The sample size was calculated using Stata 15 (StataCorp, College Station, TX, USA (34).

The sample size is not calculated for the secondary PRO outcomes. However, the principal PRO hypotheses are that the intervention will improve quality of life. A previous RCT conducted by members of our research group (8) had a comparable sample size and was able to detect an improvement in quality of life in favour of the intervention.

## **Recruitment**

The Dermatology Department will be the primary recruitment and trial site until the maximum planned number of 115 psoriasis patients has been included. Supplemental patient recruitment may be used by contact with dermatologists in practice or by advertisements in local newspapers, at public institutions or social media on the internet.

## **Assignment of interventions: allocation**

### **Sequence generation**

After baseline data has been entered in REDCap, participants will be allocated parallel-assigned 1:1 in random blocks to either the intervention or the non-intervention arm via pre-specified computer-generated block randomization in the REDCap randomization module.

### **Concealment mechanism**

The randomization code will be stored by a data manager. Furthermore, participants are informed that the purpose of the study is to investigate the effect of the prescribed topical drugs.

### **Implementation**

After informed consent has been obtained, the investigator obtains baseline data from the study participants, which will be entered in the randomization module in the electronic data collection program REDCap. The investigator will assign participants to the intervention based on the results of the randomization.

## **Assignment of interventions: Blinding**

### **Who will be blinded**

The data assessor (who measures LS-PGA and the weight of returned medication packages) will be blinded to the allocation.

### **Procedure for unblinding if needed**

Participants are not blinded to the intervention. All participants are informed that some receive additional nurse-support while others are followed by the doctor. However, the investigator tells patients the main purpose of

the trial is to study use of topical drugs, thus partially concealing the fact that this is an adherence study. Limiting participants' awareness that the main aim is to study adherence will reduce any positive effect on adherence in the non-intervention group.

## **Data collection and management**

### **Plans for assessment and collection of outcomes**

#### **Outcomes**

##### **Specification and justification of effect parameters**

LS-PGA is a validated outcome measure for the estimation of the disease activity of mild-to-moderate psoriasis (35, 36).

DLQI is a licensed validated PRO questionnaire that was first published in 1994 and has been widely used for clinical and research purposes. It has been translated into Danish (37). The domains include symptoms and feelings, work and school, daily activities, personal relationships, leisure, and treatment. The domains are divided into 10 items. Each item has a score from 0-4. The scores are added together and produce a final score from 0-30 (0, QOL not affected by skin disease, to 30, QOL severely affected by skin disease). The questions are designed to be completed within a one-week recall period (i.e., last seven days). It is designed for use in adults, i.e., patients aged 16 years and over. The average completion time of the questionnaire is two minutes, and an electronic version will be used. Usually, no assistance is required. The DLQI is self-explanatory and can be simply handed to the patient who is asked to fill it in. There is no need for detailed explanation. The DLQI will be used in accordance with its user manual. There will be no deviations from its use. The instrument has been reported to have good content and construct validity, and responsiveness in the assessment of psoriasis in adults, and can feasibly be used in clinical trials and practice (37).

EQ-5D is a validated generic licensed questionnaire for quality of life (38). There are 243 possible health states defined by combining one level from each dimension, ranging from 11111 (full health) to 33333 (worst health). Patients answer how their perceived health is on the day they complete the questionnaire. The EQ-5D-3L questionnaire also include the EQ visual analogue score (EQ VAS). The EQ

VAS records patient's self-rated health on a vertical visual analogue scale, where the endpoints are 'Best imaginable health state' and 'Worst imaginable health state'. The average completion time of the questionnaire is few minutes, and the questionnaire is cognitively undemanding. A Danish language electronic version will be used. The questionnaire will be used in accordance with the manual and no deviations from its use will be made.

Obtaining LS-PGA and DLQI five times during the study gives extra support to the analysis phase, so a smaller difference can be detected, if this is stable over time.

Primary adherence will be assessed using data from the high-quality Danish National Prescription Registry (39), which is considered valid and reliable. Using package weight to obtain an estimate of secondary adherence is considered acceptable (40). The patient-reported adherence scale has previously been used in another adherence-trial (8).

All data fields in the REDCap tool are validated: All fields have a minimum and maximum value which helps to narrow down the input options. This means that REDCap prompts an error if a field entry does not meet certain expectations. Furthermore, at end of the trial, all fields will be validated via visual checking by a member of the research staff, in order to ensure accuracy and check that all data are within the prespecified minimum and maximum values. Proxy-reported outcomes will not be used.

The REDCap data collection tool has a built-in function that issues an immediate warning if all fields in the questionnaire have not been completed. At each visit, the investigator will check that no warnings have been issued. Furthermore, PRO assessments will not be taken from participants who discontinue or deviate from the assigned intervention protocol.

#### **Data that is considered to be source data**

The following source data will be recorded from the patients' medical chart or from an interview and stored in REDCap (41): Duration of psoriasis, previous and current systemic, biologic, and topical treatment for psoriasis (in a two-year period prior to inclusion in the study) and socio-demographic data (relationship status, education and job status, municipality, and national origin). During the study, LS-PGA (including BSA) and the weight of consumed topical medication will be assessed by the blinded assessor. DLQI and EQ-5D will be reported by patients. The investigator will obtain data regarding the antipsoriatic drugs prescribed during the study period,

and the rate of filled first prescriptions for antipsoriatic drugs during the study period will be obtained. The trial personnel will note down the time used for consultations.

### **Plans to promote participant retention and complete follow-up**

All participants receive an automatically generated notification a week prior to attending in the outpatient clinic. In case of non-attendance, the investigator will contact the participant by telephone and suggest a new consultation.

### **Data management**

Study-relevant clinical data will be stored in REDCap hosted at OPEN (Open Patient data Exploratory Network). Furthermore, data obtained in the clinic will be analysed for missing data and transferred to Scientific Services at the Danish Health Data Authority for use in the economic analysis.

When participants have returned all the medication packages prescribed during the study period at week 48, the medication packages will be weighed by a blinded assessor and returned to study participants.

After the end of the study and after the reports have been submitted and approved by the authorities (the Committee on Health Research Ethics), the sponsor will ensure that the study data are deleted.

### **Confidentiality**

All data concerning participant information will be stored in REDCap and will only be accessible for staff members. All collected data will only be traceable by a code.

### **Plans for collection, laboratory evaluation and storage of biological specimens for genetic or molecular analysis in this trial/future use**

Not applicable since no biological specimens are used.

## Statistical methods

### Statistical methods for primary and secondary outcomes

#### Analysis of the primary outcome: changes in LS-PGA

Changes in LS-PGA measures from baseline to week 12 and from baseline to weeks 24, 36 and 48 will be compared between the two groups by linear mixed model for longitudinal data. LS-PGA will be presented in box plots and bar charts.

Two sensitivity analyses on LS-PGA data will be carried out in which all study participants will be included: i) a complete case analysis, and ii) an imputed analysis (after 100 times multiple imputations by multivariate normal regression on LS-PGA data) with all covariates.

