## **Objectives**

The study investigates if the use of topical corticosteroids and/or calcipotriol with a patient-supporting intervention delivered by dermatology nurses supports psoriasis patients' adherence to topical drugs

significantly 1) reduces the severity of psoriasis, 2) improves health-related quality of life, 3) improves long-term adherence to prescribed topical drugs and 4) is cost-effective compared to use of topical corticosteroids and/or calcipotriol with standard patient support.

The null hypothesis is there is no difference in reduction in severity of psoriasis (objectively as measured by the Lattice-System Physician's Global Assessment [LS-PGA]) among psoriasis patients who receive patient-supporting interventions versus those who do not receive the patient-supporting intervention (the non-intervention group). The purpose of the trial is to test the null hypothesis in a superiority setting.

Furthermore (beside the null hypothesis for the primary outcome), the study will also investigate if there is a difference in quality of life (as measured by the PRO Dermatology Life Quality Index [DLQI]), adherence to medication (as measured by filled prescriptions, amount of medication used and reported by patients in a study-specific questionnaire) and health-care costs among those receiving psoriasis patient-supporting interventions versus those who do not receive patient-supporting interventions (the PRO European Quality of life 5 Dimensions [EQ-5D] questionnaire will be obtained in order to answer this research question).

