#### **Secondary adherence**

*Specific measure:*

Secondary adherence will be calculated by combining measured amount of medication used (determined by the weight of the remains in the used medication packages) per body surface area unit affected.

Estimated recommended consumption of medication will be 0.5 gram per day multiplied by the estimated mean BSA during the whole study period, calculated from BSA measures at baseline and at weeks 12, 24, 36 and 48.

$$\text{Rate of secondary adherence} = \frac{\text{Consumed amount of topical drugs}}{\text{Expected amount used}}$$

Consumed amount of topical drugs = Sum of weight of prescribed topical drugsa – sum of weight of all prescribed medication packages returned at visit week 48b.

a: As weighed from representative full medication packages of the prescribed topical drugs.

b: By weight of medication packages returned by blinded assessor when weighed in the outpatient clinic.

Topical drugs (expected amount used) =

$$0.5 \text{ g/day} * 48 \text{ weeks} * 7 \text{ days/week} * \left( \frac{\text{BSA}(\text{baseline}) + 2(\text{BSA}(\text{W12}) + \text{BSA}(\text{W24}) + \text{BSA}(\text{W36})) + \text{BSA}(\text{W48})}{8} \right)$$

*Specific metric:*

Value at last patient visit.

*Method of aggregation:*

Mean.

*Time point:*

The rate of secondary adherence will be assessed at week 48. The measures used to calculate secondary adherence will be obtained as follows: the BSA (1 BSA equals 1% of a person's total body surface area) will be assessed at each visit (baseline, week 12, 24, 36 and 48) while weight of consumed drugs will be obtained at the last visit in week 48.

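### The primary LS-PGA analysis compares four visits without naming the contrast that decides the single superiority hypothesis, so the plan does not secure the 5% level

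*Combined protocol and SAP*

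**What the plan says.** All places are in the combined protocol and SAP.

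- **Analysis of the primary outcome:** "Changes in LS-PGA measures from baseline to week 12 and from baseline to weeks 24, 36 and 48 will be compared" between the groups by a linear mixed model. Neither the model terms nor a deciding contrast is given.
- **Objectives:** there is one null hypothesis on LS-PGA, and "The purpose of the trial is to test the null hypothesis in a superiority setting". No visit is attached to it.
- **Severity of psoriasis (outcome definition):** the metric is change from baseline, aggregated as a mean, with time points "Baseline and weeks 12, 24, 36 and 48". None is marked as primary.
- **Sample size:** a "maximum sample size for a two-sided t-test consisting of 115 participants before drop-out", at a "two-sided significance level of 95" per cent, which I read as an alpha of 5%. The visit to which the t-test applies is not named.
- **Specification and justification of effect parameters:** measuring LS-PGA and DLQI five times "gives extra support to the analysis phase, so a smaller difference can be detected, if this is stable over time". The section on secondary outcome analyses repeats the remark almost word for word.
- **Analysis of secondary outcomes:** the statistician is not blinded, and the assurance offered is that the analysis will follow the protocol's methods.
- **Sensitivity analyses of the primary outcome:** one uses "multiple imputations by multivariate normal regression on LS-PGA data) with all covariates", but no covariate list is given for LS-PGA.

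I found no multiplicity adjustment, testing order or hierarchy in the supplied text.

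**The concern.** A linear mixed model is a class of models, not a test. The same fit can give four visit-specific arm differences, an average over visits, a main effect of arm or a joint test. Each is a legitimate test of no difference in LS-PGA, and they can disagree. An unblinded statistician could follow the written plan exactly and still settle the deciding contrast after seeing results by arm. The assurance about following the protocol does not cover the one choice that determines whether superiority is claimed.

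A smaller, separate matter is precision. The outcome is change from baseline, and the plan does not say whether baseline LS-PGA is also adjusted for.

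**Working it through.** **1. The plan's own figure.** The 115 cannot be reproduced, because no LS-PGA mean or SD is given. It can be inverted. For one two-sided test at 5% with 80% power and all 115 evaluable, d = (1.960 + 0.842) × √(4/115) = 0.52. This confirms only that the sizing rests on a single test.

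**2. Inputs for the error rate.** From the documents: four post-baseline visits, a two-sided test and alpha 5% (as read above). The documents give no correlations, so these are assumed: r0 (baseline to follow-up) and r1 (follow-up to follow-up) at (0.3, 0.7), (0.5, 0.7) and (0.7, 0.8). I also assume large-sample normal tests, equal variances, equal correlations between visits and no missed visits.

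**3. Correlation between changes at two visits:** c = (1 + r1 − 2·r0) / (2 − 2·r0).

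- (0.3, 0.7): 1.1/1.4 = 0.786
- (0.5, 0.7): 0.7/1.0 = 0.700
- (0.7, 0.8): 0.4/0.6 = 0.667

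**4. Type I error by decision rule.**

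- *One contrast named in advance:* 5% by construction.
- *Average or week 48, chosen after seeing results:* the two statistics have correlation √((1 + 3c)/4) = 0.916, 0.880, 0.866. The chance that at least one exceeds 1.96 in absolute value is the error.
- *Any one of four visits significant:* 1 − ∫ φ(u) [Φ((1.96 − √c·u)/√(1−c)) − Φ((−1.96 − √c·u)/√(1−c))]⁴ du.

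| (r0, r1) | c | One named contrast | Average or week 48 | Any visit |
|---|---|---|---|---|
| (0.3, 0.7) | 0.786 | 5% | 6.9% | 11.7% |
| (0.5, 0.7) | 0.700 | 5% | 7.2% | 13.0% |
| (0.7, 0.8) | 0.667 | 5% | 7.3% | 13.5% |

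With c varied directly over 0.9, 0.8, 0.7, 0.6 and 0.5, the any-visit error is 9.4%, 11.4%, 13.0%, 14.4% and 15.6%.

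**5. Precision from baseline.** With unit variances at one visit, the change score has variance 2 − 2r and the baseline-adjusted outcome has variance 1 − r², where r is the baseline-to-follow-up correlation. The ratio is (1 − r²)/(2 − 2r) = (1 + r)/2, which is 0.65, 0.75 and 0.85 at r = 0.3, 0.5 and 0.7. The gain exists only if baseline now enters by subtraction alone. If baseline is in the outcome vector with equal means imposed on the arms, it is already there.

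**The case against.** The strongest reply is that the plan specifies one mixed model, not four tests, and gives a methods rationale for repeated measurement that fits an effect pooled over visits. The plan also commits to its stated methods. The inflation figures need either a choice made after seeing results or a success rule that appears nowhere, and every correlation is assumed.

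Much of this stands. The pooled reading is the best supported. The week 48 reading is thinner: it rests on a Discussion remark about length of follow-up and on the cost-effectiveness section, which measures gain to the end of the trial but does not govern the hypothesis test. What does not stand is that the rationale defines the test. It is a conditional remark about detectable difference, it covers DLQI equally, and it does not say what decides if the effect varies by visit.

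Three stronger readings are tempting but unsupported:

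- A reader might infer that the error rate will exceed 5%. Nothing says that several contrasts will be tried, and a single one, fixed in advance, holds 5%.
- A reader might infer that success at any visit is the planned rule. The plan neither states nor excludes it.
- A reader might take the single time point for adherence ("The rate of secondary adherence will be assessed at week 48") as a sign that the primary outcome was deliberately left open. Drug weight and self-reported adherence are collected only at that visit, so the contrast shows little.

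**Conclusion.** The gap is real and should be closed, although it is small to repair. The supplied text names neither a deciding contrast nor a multiplicity rule for the primary outcome, so the 5% level is not secured. The possible cost is conditional: about 7% if the average or week 48 is chosen after seeing results, and about 9% to 16% under an any-visit rule. Both rest on assumed, equal correlations and no missed visits. Baseline handling is a matter of precision only: either approach, fixed in advance, holds 5% for a named contrast.

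The finding of absence covers the supplied text. Some pages were removed before review, and the registry entry was not available.

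**What to change.** Before LS-PGA is analysed by arm:

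1. Name one primary contrast from the mixed model, tested at two-sided 5%. It can be the average arm difference over weeks 12 to 48, which is closest to the plan's own rationale for repeated measurement, or the week 48 difference. Label the other visit contrasts supportive.
2. State the model terms: arm, visit and arm-by-visit, with baseline LS-PGA as a covariate or with baseline means constrained equal between arms.

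No new data are needed, since baseline LS-PGA is already collected. Enrolment began in June 2020, so an amendment may be needed, and the protocol requires ethics approval before a substantial one takes effect. The sponsor gives up a superiority claim based on one favourable visit. An average dilutes an effect that appears late, while week 48 alone forgoes the gain from averaging. Which has more power depends on how the effect develops, the correlation pattern and missed visits, so no general threshold is offered.

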#### Analysis of secondary outcomes: changes in DLQI value and adherence

Changes in DLQI measures from baseline to weeks 12, 24, 36 and 48 will be compared between the two groups by linear mixed model for longitudinal data. DLQI will be presented in box plots and bar charts.

For separate analyses of the three adherence measures (by filled prescriptions, weight of medication and patient reported adherence, respectively), the adherence rate is dichotomized with a selected cut-off of 80%, with adherence rates above 80% considered adherent (a cut-off typically used when studying adherence in chronic diseases) (8, 42). Dichotomized adherences are compared by using logistic regression.

Statistical analysis will be conducted by an experienced statistician. The statistician will not be blinded to the intervention, as any blinding would be difficult to obtain because the participants in the intervention group are subdivided in three different subgroups (grouped according to the nurse delivering the intervention), while the non-intervention group is kept in one group. However, the analysis will comply with the statistical methods outlined in the study protocol. An interim analysis is not planned.

Obtaining LS-PGA and DLQI five times during the study gives extra strength to the analysis, so a smaller difference can be detected, if this is stable over time.

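### The mixed models for change in LS-PGA and DLQI specify no baseline adjustment, so they give up precision that could be had at no cost

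*Combined protocol and SAP*

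**What the plan says.** The Severity of psoriasis section gives the metric as change from baseline, aggregated as a mean, with assessments at baseline and weeks 12, 24, 36 and 48. The primary analysis section then says: "Changes in LS-PGA measures from baseline to week 12 and from baseline to weeks 24, 36 and 48 will be compared" between the groups by a linear mixed model. It gives no fixed effects, covariance structure, baseline term, equal-baseline constraint or primary visit. Covariates are mentioned only for the imputed sensitivity analysis and are not listed there.

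The secondary analysis section follows the same pattern: "Changes in DLQI measures from baseline to weeks 12, 24, 36 and 48 will be compared between the two groups", again by linear mixed model.

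The Sample size section does not refer to the mixed model. It says "A relative 20% difference in mean scale on the LS-PGA is expected" and continues: "Based on mean and standard deviations of LS-PGA from the previous study this results in a maximum sample size for a two-sided t-test". No mean, SD or correlation is printed.

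Elsewhere the plan does adjust for baseline: under Cost-effectiveness analyses, the QALY comparison is adjusted for baseline utility and the cost comparison for earlier costs.

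**The concern.** A change score subtracts the whole baseline value, whatever its correlation with follow-up. When r is below 1 that subtracts too much, which adds noise and favours the arm that happened to start worse. A mixed model does not cure this by itself. If baseline is one of the responses and each arm has its own baseline mean, the usual arm-by-visit contrast with complete data equals the change-score contrast. Adjustment arises only if baseline is a covariate or the arms share one baseline mean, and neither is stated.

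Three features make this worth settling. Entry covers mild to severe disease, including patients on stable systemic drugs, and the Sequence generation section names no stratification factor, so baseline LS-PGA can differ between arms by chance. The statistician is unblinded, and the stated safeguard is compliance with the methods in the protocol, which leave this choice open. Finally, the sizing is worded in terms of LS-PGA itself while the analysis concerns change, so the planned power is not tied to the planned analysis.

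**Working it through.** **Inputs from the Sample size section.** Power 80%; alpha two-sided, written as a "two-sided significance level of 95" per cent and read here as 0.05; "1:1 allocation is desirable"; and a "maximum sample size for a two-sided t-test consisting of 115 participants before drop-out".

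**Assumed, because the documents do not give them.** r between 0.1 and 0.7; the same SD s at every visit; compound symmetry for the four-visit average; a treatment effect that is constant over visits.

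**The plan's own figure.** The 115 cannot be reproduced without the mean and SD. Working backwards with d = (1.960 + 0.842) × √(2/n) for n per arm:
- If 115 already includes 20% dropout (92/0.8 = 115; an inference, since the text prints 80%), n = 46 and d = 0.584.
- If 115 is the number analysed, n = 57.5 and d = 0.523.

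The power figures below are the same for either n, because each starts from exactly 80% on levels.

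**Variance per patient, in units of s².**
- Level at one visit: 1.
- Change at one visit: 2(1−r). Adjusted: 1−r². Ratio: 2/(1+r).
- Mean change over four visits: (1+3r)/4 + 1 − 2r = 1.25(1−r). Adjusted: (1+3r)/4 − r² = (1−r)(1+4r)/4. Ratio: 5/(1+4r).

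A generalised least squares calculation for a five-visit model gives the same values. At r = 0.3, free baseline means give 1.40 (week 48) and 0.875 (average); one common baseline mean gives 0.91 and 0.385.

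**Power** = Φ(2.802/√variance − 1.960):

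| r | Change, one visit | Adjusted, one visit | Change, four-visit average | Adjusted, four-visit average |
|---|---|---|---|---|
| 0.1 | 55% | 80% | 75% | >99% |
| 0.2 | 60% | 82% | 80% | >99% |
| 0.3 | 66% | 84% | 85% | >99% |
| 0.4 | 72.5% | 86% | 90% | >99% |
| 0.5 | 80% | 90% | 94% | >99% |
| 0.7 | 95% | 97.5% | >99% | >99% |

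**Thresholds.** Change does worse than a single-visit level when 2(1−r) > 1, that is r < 0.5, or for the four-visit average when 1.25(1−r) > 1, that is r < 0.2.

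**Variance ratios.** One visit: 2/1.3 = 1.54 at r = 0.3 and 2/1.5 = 1.33 at r = 0.5. Four-visit average: 5/2.2 = 2.27 and 5/3 = 1.67. For 80% power at one visit with r = 0.3 and d = 0.584, change needs 46 × 1.40 = 64.4, so 65 per arm; the adjusted analysis needs 46 × 0.91 = 41.9, so 42.

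**Unequal SDs** (s0 at baseline, s1 at follow-up). Change has variance s0² + s1² − 2r·s0·s1 and adjusted has s1²(1−r²). The difference is (s0 − r·s1)², which is never negative. So adjustment still does not lose, apart from the small cost of estimating the slope. The change-versus-level threshold becomes r = s0/(2·s1), so 0.5 is not a fixed number.

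**Chance imbalance.** With equal SDs, a baseline difference D between arms moves the unadjusted contrast by −(1−r)D. At 46 per arm, one standard error of D is √(2/46) = 0.21 SD. At r = 0.3 this moves the contrast by 0.7 × 0.21 = 0.15 SD, against a target of 0.58 SD.

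**The case against.** The strongest reply is that the plan is silent about baseline rather than opposed to adjusting for it. It counts LS-PGA and DLQI as measured five times, so baseline may be one of the modelled responses, and with a common baseline mean such a model is as efficient as covariate adjustment. That stands as a possibility. But the text does not state the constraint, the outcome is defined as change, and free baseline means give the change-score result.

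A reader might also infer that the trial loses its 80% power whenever r is below 0.5. The documents do not support that. The 0.5 figure applies to one visit with equal SDs. The plan names no primary visit and expects the repeated measurements to detect a smaller difference; for the four-visit average the figure is 0.2. Nothing in the documents places r below either value, and above 0.5 the single-visit change score beats the level. Nor is it settled that the sizing used the SD of levels. That is the natural reading, but the same section also speaks of improvement in LS-PGA; if the SD was of change, the mismatch disappears.

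Two limits also stand. The unadjusted contrast is unbiased under randomisation, and its type I error is not in question. And the plan says the sample size was not calculated for the secondary patient-reported outcomes, so for DLQI this concerns precision only.

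**Conclusion.** The point holds as one of efficiency and specification: a free improvement, not an error that invalidates the trial. As written, the LS-PGA and DLQI comparisons are unadjusted change contrasts. Under equal SDs and r below 1, baseline adjustment is more precise. Over r = 0.3 to 0.5 the unadjusted variance is larger by a factor of 1.54 to 1.33 at one visit, and 2.27 to 1.67 for the four-visit average. The latter range also rests on compound symmetry.

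A shortfall below 80% power is conditional and not demonstrated. It requires that the sizing SD was of levels, and r below 0.5 (single visit) or below 0.2 (four-visit average). The documents give no r, mean, SD or primary contrast from which to decide.

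**What to change.** In the LS-PGA and DLQI analysis sections, fit the mixed model to weeks 12, 24, 36 and 48 with arm, visit, arm-by-visit, baseline value and baseline-by-visit. Alternatively, fit all five visits with the two arms constrained to one baseline mean. Name the primary contrast: one visit, or the average over the four.

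In the Sample size section, say that the 80% comes from an unadjusted two-sample t-test on LS-PGA, and state whether the SD was of level or of change. Print that SD, the mean and any correlation assumed. Do not relabel the 80% as the power of the baseline-adjusted comparison: on the single-visit figures above, that power would be 82% to 97.5% for r from 0.2 to 0.7.

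The cost is wording only. Baseline LS-PGA and DLQI are already collected before randomisation, and no visit, measurement or patient is added. Because the statistician is unblinded, the change should be dated before outcome data are analysed.
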